Pilot study to evaluate the efficacy of Ostom-i alert system at decreasing dehydration related complications in patients with new ileostomies.

Principal Investigator:

[name], M.P.H.

Co-Investigator:

[name], M.P.H.

Table of Contents

A.	Abstract	3
B.	Background/Significance.	3
C.	Specific Aims.	4
D.	Methodology	5
E.	Data Analysis	7
F.	Potential Benefits and Risks, Monitoring and Quality Assurance	8
G.	Appendix E: Complication/unanticipated event form.	17
Н.	Appendix F: References	18

A. Abstract

B. Background/Significance

Ileostomy creation is a common surgery performed in patients who have disease or injury to their colon requiring fecal diversion. The most common causes for ileostomy surgery include Crohn's disease, ulcerative colitis, colon and rectal cancer. Less common causes include bowel obstruction and familial polyposis. Ileostomy formation can be temporary, and is often used to protect anastomoses in colorectal resections. It can also be permanent, when disease or injury is more extensive. All patients undergoing an ileostomy face unique post-operative challenges due to the alteration of absorption and waste elimination pathways. Prior to surgery, patients are counseled about these challenges including the expected increase in frequency of liquid stools, which can have both bothersome and more serious complications.

Hospital readmissions in people who have recently undergone colon and rectal surgery are frequent, and can be costly and delay post-operative healing (Nagle, 2012). Current NSQIP colectomy readmission rates for open and laparoscopic colectomies over the past 12 months at Massachusetts General Hospital were 11.3% and 10.9% respectively. Average national readmission rates for open and laparoscopic colectomies over the past 12 months were 13.2% and 10.7% respectively. The most common reason for hospital readmission following surgery is dehydration, with other causes including infection, bowel obstruction, bleeding, wound dehiscence with leak, and pain (Nagle, 2012).

Dehydration is a serious but preventable complication in patients with new ileostomies. Even small changes in fluid intake or output can cause body fluid imbalances that promote dehydration and necessitate IV rehydration (Messaris, 2012). Previous research has shown that the use of pre-operative teaching, direct patient engagement from post-op day one, engaging patients to perform self-care for their stoma during hospitalization, and having patients track intake and output post-discharge can decrease readmission rates (Nagle, 2012). With implementation of this pathway over the course of 7 months, there was a decrease in the overall 30- day postdischarge readmission rate for patients with new ileostomies from 35.4% to 21.4%, with the rate for dehydration alone falling from 15.5% to 0% (Nagle, 2012).

The Ostom-i alert (OIA) is a discrete novel device which clips onto any ostomy bag from edge to edge and measures the horizontal tension between the edges over time, as a result of stool volume in the ostomy. It is an FDA approved medical device.

Until now, the OIA has been mainly used to warn patients when the ostomy bag is at risk of overflow thereby reducing the risk of leakage causing embarrassment to the patient and caregivers. It can also be used to evaluate the overall output of the ostomy. When patients leave the hospital, the OIA data is sent to the patient's smartphone through bluetooth technology and can be viewed on the internet in real time by the surgical team (stoma nurse, surgeon, clinical research staff). This would allow patients to monitor their output more accurately and allow them to contact clinical staff with questions or to help with bowel management when output is outside of established parameters (too little or too high output).

While all patients with ileostomy have a risk of dehydration, early identification of those at greater risk may lead to home intervention and decreasing hospital readmission. Decreased readmissions ultimately leads to faster post-operative recovery, decreased risk of sequela of readmission (nosocomial infection, pneumonia etc) and decreased healthcare costs.

C. Specific Aims

Study Aims

The aim of the study is to evaluate the efficacy of the Ostom-i device in decreasing readmission rates of subjects in the first 30 days post-operatively.

Hypothesis:

We hypothesize that readmission rates will decrease with use of Ostom-i device.

Primary Outcome:

To demonstrate a reduction in readmission of patients with new ileostomies.

D. Methodology

I. Subject Selection

All patients over the age of 18 undergoing procedures with new ileostomy creation at MGH will be offered the opportunity to take part in the trial. We plan to recruit 30 subjects for Ostomimonitoring. Once subjects have consented to participate in the trial, they will be educated about the use of the OIA device and smartphone application as well as the discharge instructions. Specific eligibility criteria for participation in the study include: greater than 18 years of age, English speaking, creation of new ileostomy, access to smartphone with bluetooth technology to support OIA application, and must be able to give written consent.

II. Subject Enrollment

All patients who undergo new ileostomy creation at MGH first meet with the ostomy nurses preoperatively, for an educational session and stoma marking, as per standard of care. All patients scheduled to undergo ileostomies will be offered the opportunity to participate in the study by research nurses. If patients are interested in participating in the study, they will be approached again 24 hours after their surgery, during their first stoma teaching session. Those who wish to participate will be offered the opportunity to ask any questions about the protocol and then sign consent. We will have a total of 30 subjects enrolled and using the device.

III. Study Procedures

Once appropriate IRB approved consent has been given, subjects will be given device and assisted in setting up the OIA app. They will be given education about parameters for ostomy output. All subjects will have additional teaching of specific monitoring parameters and education about the device.

Once subjects are trained on the device, they will monitor outputs on a daily basis including during initial hospitalization until 30 days post-op. Outputs will be recorded by the Ostom-i application, which will be shared via bluetooth technology with the surgeon and research nurses in real time. If outputs are less than 250mL or greater than 1200mL per day, subjects will be alerted by system and subjects will be instructed to call their surgeons who will adjust their medications and fluids accordingly.

Subjects will be monitored until the 30 day post-operative period is completed. Any phone calls to office due to high or low output will be documented. All patients are seen as standard of care by their treating physician and stoma nurses at 4-6 weeks post op. Any readmissions to outside hospitals are documented at the post-op visits.

E. Data Analysis

Intent-to-treat:

While a randomized study design is ideal, due to financial limitations, we are limited to 30 devices and therefore plan to treat a single cohort of 30 patients. The primary analysis outcome will be readmission rate for dehydration, and the analysis of this outcome will utilize an intent-to-treat analysis population including all 30 patients. Established readmissions rates will be used as a historical control group to compare readmission rates. Confounding will be minimized

because subjects will be treated per standard of care in addition to receiving education about the Ostom-i device.

Given previous studies suggesting that more awareness leads to a decrease of admission to 0% (Nagle, 2012), we expect that there will be no more than one readmission among these 30 patients. The study has 90% power to rule out a readmission rate for dehydration $\geq 15\%$ in favor of a significantly reduced rate of $\leq 2\%$ with p ≤ 0.05 by using an exact test.

If the study results appears promising (i.e., no or only one readmission), given the very low risk to patients, a larger scale randomized controlled trial will be considered by requesting additional funding.

F. Potential Benefits and Risks, Monitoring and Quality Assurance

I. Benefits

It is hoped that the OIA device will be able to provide more accurate real-time monitoring of ostomy output that will ultimately reduce readmission rates due to dehydration by allowing better management of fluids and hydration post-operatively. The results of this study may benefit future subjects long-term by allowing subjects access to technology which will influence the post-op treatment of dehydration and fluid imbalance following ileostomy surgery.

II. Risks and discomfort

This is a pilot study in which subjects will be followed by standard of care post-operative management with the exception that Ostom-i subjects will have a way to measure and transmit their stoma output to their provider in real time. This in theory should decrease subjects risk for dehydration. Subject data including outputs, phone calls, and any hospital admissions or EW visits for hydration will be shared with the surgeon/NP and documented. All subjects have the option to refuse or discontinue participation at any point during the study. Medical records and research materials will be kept confidential and in a password protected database. Subjects will be followed for post operative management as per standard of care.

The OIA device is discrete and is worn over the ostomy bag, underneath the subject's clothing. Subject information will only be shared with the subject's providers (MD, NP) and with the researchers participating in this study.

III. Monitoring and Quality Assurance

Monthly meetings will be organized to allow monitoring of recruitment of subjects, and to assure adherence of the IRB protocols. Unanticipated problems involving risks to subjects or others, including adverse events will be reported to the PHRC in accordance with PHRC reporting guidelines within 5 working days or 7 calendar days of the date the investigator first becomes aware of the problem. Accuracy and completeness of data collection, case report form entries, source documents and informed consent will also be reviewed. IRB will be notified of any major unforeseen complications associated with the study.

G. Appendix E: Case Report Forms				
Complication/Unanticipated Event				
SUBJECT NO.				
DATE OF SUR	GERY:			
DATE OF DISC	CHARGE:			
DATE OF 30 D	AYS POST-OP:			
Follow-up Inter ☐ Screening	val: ☐Post-operative period ☐ 4-6 week pos	t-op visit.		
List any o	complaints, adverse reactions, or proble	ms noted by subject below.		
	Details of event	Intervention		

Patient Phone Log	2			
SUBJECT NO.		NITIALS:		
DATE OF SURGI	ERY:			
DATE OF DISCH	IARGE:			
DATE OF 30 DAYS POST-OP:				
Total output A	Action taken	Date of	Resolution	Caller

Date of phone conversation	Total output (in mL) in last 24hr prior to call	Action taken	Date of follow-up phone conversation	Resolution	Caller

30 D	30 Day Post-Operative Report					
SUB						
DAT						
DAT	DATE OF DISCHARGE:					
DATE OF 30 DAYS POST-OP:						
Date of appointment	Outcome	Provider Plan	Name of Provider Answering			

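### The trial counts readmissions to 30 days after surgery, but its unsourced 15% null probably comes from a 30-day postdischarge rate; if so, the comparison leans towards the device by an uncertain amount.

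*Combined protocol and SAP*

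**What the plan says.** Four places set the time frame from surgery. The aim in Section C is "decreasing readmission rates of subjects in the first 30 days post-operatively". Under Study Procedures (Section D. III), after training on the device "they will monitor outputs on a daily basis including during initial hospitalization until 30 days post-op". The same section says "Subjects will be monitored until the 30 day post-operative period is completed". The case report forms carry a date for post-operative day 30.

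Section E states that "The primary analysis outcome will be readmission rate for dehydration". It tests this against a null of 15% or more with an exact test and gives neither a window nor a source for the 15%. The comparator is described only in general terms: "Established readmissions rates will be used as a historical control group to compare readmission rates". The Primary Outcome statement in Section C has no window either.

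The only dehydration readmission rate in the document is in Section B, which reports a "decrease in the overall 30- day postdischarge readmission rate for patients with new ileostomies from 35.4% to 21.4%, with the rate for dehydration alone" going from 15.5% to 0%. Section E cites the same study for its expectation of 0%. The other readmission figures in Section B (10.7% to 13.2%) are for colectomy and are not dehydration rates.

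**The concern.** A readmission can occur only after the index discharge. A window that closes on post-operative day 30 therefore gives each subject 30 days minus the index stay at risk. A 30-day postdischarge rate gives every patient 30 days. If the null is such a rate, the trial would be expected to see fewer events than the null implies, even with a device that does nothing.

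This matters because the study has one arm, and the comparison with the historical rate is its only comparison. The decision turns on whether there are no more than one readmission among 30 subjects, and that rule has almost no slack at 15%.

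**Working it through.** **Inputs from the document.** n = 30; null 15%; alternative 2%; significance level 0.05; exact test; promising result = 0 or 1 readmission (all Section E). Cited dehydration rate 15.5% (Section B).

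**Inputs assumed.** The document gives neither the index stay nor the timing of readmissions. I take stays L of 4, 5, 7 and 10 days, and either a constant hazard after discharge or a hazard that halves every h = 3, 5, 7 or 10 days. None of these shapes is favoured.

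**Step 1: the plan's own figures.** With X the number of subjects readmitted, P(X ≤ 1) = (1−q)^30 + 30q(1−q)^29.

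- At q = 0.15: 0.0076 + 0.0404 = 0.0480, so the rule meets 5% one-sided.
- At q = 0.155: 0.0416.
- At q = 0.02: 0.5455 + 0.3340 = 0.8795. The stated power is 90%; this small gap is a separate matter.

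**Step 2: slack in the rule.** P(X ≤ 1) = 0.05 at q = 0.1486. A no-effect rate only 0.14 percentage points below 15% takes the error past 5%.

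**Step 3: no-effect rate in the trial's window.** Suppose p is a 30-day postdischarge rate and events are cut at post-operative day 30.

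- Constant hazard: q = 1 − (1−p)^((30−L)/30). For p = 0.15 and L = 7: 1 − 0.85^(23/30) = 0.1171, and P(X ≤ 1) = 0.1186.
- Half-life h: q = 1 − exp[ln(1−p) × f], with f = (1 − 2^(−(30−L)/h)) / (1 − 2^(−30/h)). For p = 0.15, L = 7, h = 7: f = 0.946, q = 0.1425, and P(X ≤ 1) = 0.0594.

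**Step 4: one-sided error of the 0-or-1 rule, L = 4 to 10 days.**

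| Event timing | From 15% | From 15.5% |
|---|---|---|
| Windows matched | 4.8% | 4.2% |
| Constant hazard | 8.1% to 17.2% | 7.2% to 15.7% |
| Half-life 10 days | 5.8% to 8.4% | 5.0% to 7.4% |
| Half-life 7 days | 5.3% to 6.9% | 4.6% to 6.0% |
| Half-life 5 days | 5.0% to 5.8% | 4.4% to 5.1% |
| Half-life 3 days | 4.8% to 5.0% | 4.2% to 4.3% |

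Error rises above the matched value in every row, so the direction is the same throughout. The size depends on how early readmissions occur. From 15.5%, 5 of the 12 combinations with half-lives of 5 to 10 days stay below 5%. With a half-life of 3 days, none exceeds 5% from either starting rate.

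**The case against.** The strongest reply is that the window is not in doubt: four consistent statements point to 30 days after surgery and nothing states another. That stands, and repeating the window in Section E would be only a drafting improvement. But it leaves the other half of the comparison open, namely which window the 15% refers to.

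A second reply is that the link to the postdischarge rate is an inference. Section E names no source, and Section B applies the word postdischarge to the overall rate, with the dehydration rate following in the same sentence. This also stands, and the directional claim is therefore conditional.

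A third reply is that the size rests on assumed stays and timing, and with early enough events the error never passes 5%. That is correct.

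A reader might also infer that the outcome window runs to the clinic visit, because "All patients are seen as standard of care by their treating physician and stoma nurses at 4-6 weeks post op" and "Any readmissions to outside hospitals are documented at the post-op visits". On that reading the bias could change sign, or every event could be cut off at day 28. The text does not support this. The visit is a means of learning about admissions to outside hospitals, not a statement of the outcome window, and subjects are separately followed to day 30.

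Finally, the protocol itself concedes that randomization would be better, and a result of 0 or 1 leads only to considering a randomized trial. That limits the consequence but does not remove the mismatch.

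**Conclusion.** The point holds as a mismatch in the text: a 30-day post-operative window on the trial side, and on the null side an unsourced 15% whose only visible origin is given within a 30-day postdischarge rate. Confidence in this is high.

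If that rate is the source, the comparison leans towards the device. By how much is uncertain. Across the assumed stays and event timings, the error runs from about the nominal 5% or slightly below to 17.2% (from 15%) or 15.7% (from 15.5%). A reader might conclude that the test is shown to be invalid, or that its true error is near 17%; the document supports neither, since it gives no index stay, no event timing and no source for the null. It should be put right before the data are seen, in proportion to a pilot whose result leads only to considering a further trial.

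**What to change.** In Section E, state the source and window of the 15% null, and define readmission for dehydration over that same window.

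- **If the null is the 30-day postdischarge rate:** count from index discharge through 30 days after discharge and change the form date to match. Confirm status at that date at the 4-6 week visit, or by a call or record check when the visit comes earlier. For the assumed stays the date is post-operative day 34 to 40, and the visit falls on day 28 to 42. Report events before and after post-operative day 30 separately, because device monitoring ends then.
- **If the null is a 30-day post-operative dehydration rate:** keep the post-operative window and state that later events recorded at the visit are not counted.

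The source must be settled first. Pairing a post-operative null with a postdischarge outcome makes the opposite mismatch. With q = 1 − (1−p)^(30/(30−L)), constant hazard and stays of 4 to 10 days, error falls to between 2.6% and 0.6% and power to between 84.9% and 77.5%.

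**Cost.** The second option is wording only if 15% is already a post-operative rate. If the null is instead replaced by one below 14.86%, the test must be recomputed: one readmission would no longer be significant, and with 0 of 30 as the only success, power at 2% is 54.5%. The first option needs a form change, outcome follow-up longer by each subject's index stay, and some calls or record checks, with no extra devices or subjects. Its downside is that events on late, unmonitored days count against the device, hence the separate reporting.

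### The aim is to reduce 30-day readmission, but section E analyses only readmission for dehydration, so the study could be called promising without an all-cause result

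*Combined protocol and SAP*

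**What the plan says.** All references are to the combined protocol and SAP.

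- **Aim and outcome (section C).** The aim is to "evaluate the efficacy of the Ostom-i device in decreasing readmission rates of subjects in the first 30 days post-operatively". The hypothesis is likewise about readmission rates, and the primary outcome is "a reduction in readmission of patients". None of the three names a cause.
- **Intervention (section D.III).** "If outputs are less than 250mL or greater than 1200mL per day, subjects will be alerted by system". Low and high output both trigger action, and that action is a call followed by a change in treatment: "subjects will be instructed to call their surgeons who will adjust their medications and fluids accordingly".
- **Analysis (section E).** "The primary analysis outcome will be readmission rate for dehydration". The power statement sets a dehydration rate of 15% or more against one of 2% or less, with 90% power and p ≤ 0.05 by an exact test. The design is to "plan to treat a single cohort of 30 patients" against historical rates. The result is promising if there is no readmission or only one; this sentence does not repeat the word dehydration.
- **Background (section B).** Dehydration is given as the commonest reason for readmission, with "other causes including infection, bowel obstruction, bleeding, wound dehiscence with leak, and pain". In the cited pathway study, 30-day post-discharge readmission fell "from 35.4% to 21.4%, with the rate for dehydration alone falling from 15.5% to 0"%.
- **Recording (sections D.III, F and the case report forms).** Calls for high or low output, outside-hospital readmissions, complications and adverse events are documented or reported.

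**The concern.** The study asks whether the device reduces readmission, and the intervention is wider than dehydration: it responds to low output too, and each alert can lead to a change in treatment. The only planned analysis is of one cause. A readmission for anything else, whether unrelated to the device or following an alert-driven change, has no planned estimate, comparator or place in the decision.

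A small dehydration count would then support considering a larger randomised trial, although the study had not shown that readmission, the quantity named in its aim, was lower. Section E also rests that step on very low risk to patients, yet it plans no look at readmissions after alert-driven changes.

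**Working it through.** **Inputs.** N = 30, null rate 15%, alternative rate 2%, p ≤ 0.05, stated power 90%, and the rule of at most one readmission (all section E). All-cause readmission 35.4% before and 21.4% after the pathway; dehydration readmission 15.5% before and 0% after (section B).

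**Step 1. Reproduce the plan's figure.** For an exact binomial rule of at most one event in 30,

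P(X ≤ 1) = (1 − p)^30 + 30 p (1 − p)^29.

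- p = 0.15: 0.0076 + 0.0404 = 0.048, which meets p ≤ 0.05 one-sided.
- p = 0.02: 0.5455 + 0.3340 = 0.879, against the stated 90%. The gap is about 2 percentage points, minor and separate from this point.

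So the rule of at most one matches the dehydration calculation.

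**Step 2. Apply the same rule to readmission for any cause.**

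- p = 0.214 (cited all-cause rate after the pathway): 0.0007 + 0.0060 = 0.007.
- p = 0.219 (2% dehydration plus 19.9% other causes, from step 3): 0.006.

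Read as all-cause, the rule would almost never be met, even at the improved rate in the cited study. It is workable only as a dehydration rule.

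**Step 3. What the dehydration reading leaves out.** Assume that each readmission has one cause.

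- Before: 35.4 − 15.5 = 19.9% for other causes; 30 × 0.199 = 6.0 per 30.
- After: 21.4 − 0 = 21.4% for other causes; 30 × 0.214 = 6.4 per 30.

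With the dehydration rate held at 2%, the chance of a promising result stays at 0.879 whatever the rate of other readmissions.

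**Step 4. Precision of an all-cause result.** If 6 of 30 subjects were readmitted for any cause (20%), the exact (Clopper–Pearson) 95% interval is 7.7% to 38.6%. It contains both 21.4% and 35.4%, so the result would be descriptive rather than a test.

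**The case against.** The strongest reply is that dehydration is not the only outcome in the document. Section C names readmission generally, and the promising rule, taken literally, would count a readmission for obstruction against the device. That is correct as to wording. It does not settle the matter: section E states a cause-specific primary analysis and powers it, and the literal all-cause rule is close to unattainable (step 2).

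A second reply is that a cause-specific endpoint suits a pilot whose title is about dehydration-related complications, and that a promising result leads only to a further trial being considered. This also stands. It supports keeping dehydration as the primary analysis; it is no reason to leave the all-cause result out.

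A reader might infer four stronger things that the documents do not support:

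- **That other readmissions go unseen.** Calls, outside readmissions, complications and adverse events are all recorded or reported. What is missing is a planned analysis.
- **That any harm from an alert-driven change escapes the count.** A dehydration readmission after such a change would count under section E.
- **That low output stands for obstruction.** Section B lists obstruction as a cause of readmission; nothing ties it to output below the lower alert limit.
- **That preventing dehydration moves readmissions to other causes.** The change from 19.9% to 21.4% is a derived difference of 1.5 points, or 0.45 of a subject in 30. It comes from an education pathway and no group sizes are given. It is no evidence of a shift and none about this device.

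**Conclusion.** The point holds as a gap in the planned analysis. Sections C and E define different outcomes, and the decision rule fits only the narrower one: 0.879 at 2% dehydration readmission, against 0.007 at 21.4% all-cause. Followed that way, the plan permits a promising result with no planned estimate of the quantity in its aim.

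The size of what is left out, about 20% or roughly 6 subjects in 30, is illustrative. It assumes one cause per readmission, and the cited rates count from discharge whereas this study counts 30 days from surgery.

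The documents do not show that the device raises other readmissions or that harm would be hidden. This is a cheap improvement to a pilot; it does not make the dehydration analysis invalid.

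**What to change.** In section E:

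1. State that the rule of at most one event refers to readmission for dehydration, and reconcile section C with this.
2. Add 30-day all-cause readmission as a key secondary outcome, with an exact 95% confidence interval.
3. List each readmission by cause, including obstruction or ileus, and note whether a low- or high-output alert and a resulting change came before it.
4. Require the all-cause result to be reported and considered beside the dehydration count before the study is called promising.

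A fixed all-cause limit is not recommended. A limit of 10 of 30, for example, just under 35.4%, would be met with probability 0.49 at a true rate of 35.4% and 0.96 at 21.4%, so it would discriminate poorly.

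The cost is a little more analysis and probably a cause-of-readmission field, since the case report forms as reproduced show none. No extra subjects or visits are needed. The all-cause interval will be wide (step 4) and should be presented as descriptive.

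### The reason given for minimized confounding does not make this cohort comparable with historical patients, and a good result cannot isolate the device or establish its efficacy

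*Combined protocol and SAP*

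**What the plan says.** Section E (Data Analysis) plans a single cohort of 30 and compares its dehydration readmission rate with established historical rates. It concedes that randomization would be ideal and gives the supply of devices as the limit. It then states that confounding will be minimized "because subjects will be treated per standard of care in addition to receiving education about the Ostom-i device". The test is exact, against 15%. No or one readmission counts as promising and would lead the sponsor to consider a randomized trial.

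Other sections bear on comparability:

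- **Follow-up.** Section D.III: "Subjects will be monitored until the 30 day post-operative period is completed". The aim in Section C uses the same post-operative window.
- **Historical figures.** Section B reports, for a teaching and tracking pathway, "a decrease in the overall 30- day postdischarge readmission rate for patients with new ileostomies from 35.4% to 21.4"%, and in the same sentence "with the rate for dehydration alone falling from 15.5% to 0"%. It says of the pathway's elements, which include pre-operative teaching, that "having patients track intake and output post-discharge can decrease readmission rates". No device is mentioned.
- **Eligibility.** Section D.I requires "English speaking, creation of new ileostomy, access to smartphone with bluetooth technology to support OIA application", as well as written consent.
- **Teaching.** Section D.III: "All subjects will have additional teaching of specific monitoring parameters and education about the device". Section D.II says that a preoperative educational session is already standard at this site.
- **Description of care.** Section F.II says that management is standard "with the exception that Ostom-i subjects will have a way to measure and transmit their stoma output to their provider in real time".

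**The concern.** In a single-arm study with a historical comparator, confounding depends on whether the new patients would have had the historical rate without the intervention. Giving them standard care plus device education does not settle that. The plan describes no matching, covariate adjustment or contemporaneous site data that would.

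The stated aim is the efficacy of the device. If the sentence stands, a reader or funder could take 0 or 1 of 30 as evidence that the device lowered readmissions, with confounding already handled. What the result can support depends on the background rate for comparable patients over the same window, and on what the intervention consisted of.

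**Working it through.** **Inputs.** From Section E: n = 30, null rate 15%, alternative 2%, p ≤ 0.05, exact test, promising if 0 or 1. From Section B: historical dehydration rate 15.5% before the pathway, 30-day post-discharge window. From Sections C and D.III: trial window of 30 days from surgery. Length of stay is not given, so 3, 5, 7 and 10 days are assumed.

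**The plan's own figures.** With X ~ Binomial(30, p), P(X ≤ 1) = (1−p)^30 + 30p(1−p)^29.

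- p = 0.15: 0.0480, so the 0-or-1 rule meets 0.05 one-sided.
- p = 0.02: 0.879. The plan states 90%; the gap of about 2 points is a separate, minor matter.
- Sidedness is not stated. The two-sided exact p-value for 1/30 is 0.076, so the rule fits only a one-sided test, which is used below.

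**What each result excludes.** The exact (Clopper-Pearson) one-sided 95% upper limit solves P(X ≤ x) = 0.05.

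- 0/30: 1 − 0.05^(1/30) = 9.5%.
- 1/30: the root of (1−p)^30 + 30p(1−p)^29 = 0.05 is 14.9%.

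A result therefore supports a reduction only if the comparable background rate lies above the limit for that result.

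**The window.** Days in hospital before discharge cannot produce a readmission. With a stay of L days, the trial observes 30 − L days after discharge, while the cited figures cover 30. If 15.5% accrued at a constant rate, the comparable rate is q = 1 − (1 − 0.155)^((30−L)/30), and P(0) = (1−q)^30 = 0.845^(30−L).

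| Assumed stay L (days) | Comparable rate q | P(0 or 1), no effect | P(0), no effect |
|---|---|---|---|
| none (15.5% as cited) | 15.5% | 4.2% | 0.6% |
| 3 | 14.1% | 6.3% | 1.1% |
| 5 | 13.1% | 8.2% | 1.5% |
| 7 | 12.1% | 10.7% | 2.1% |
| 10 | 10.6% | 15.7% | 3.4% |

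Every adjusted rate lies below 14.9%, so 1/30 would no longer exclude the background. Every adjusted rate lies above 9.5%, so 0/30 still would. If readmissions cluster soon after discharge, the shift is smaller than shown.

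**The other threats, from the text.**

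- *Selection.* The documents do not say that the historical patients were restricted to consenting English speakers with a suitable phone. The size and direction of any bias are unknown.
- *The 15% itself.* It is close to the cited 15.5%, which is a pre-pathway rate. This site already gives preoperative education as standard, and no dehydration rate for the site is given. Its only rates (11.3% and 10.9%) are readmissions after colectomy, a different outcome and population.
- *Teaching.* All subjects receive teaching on output parameters along with the device. Section B credits teaching and tracking without this device with a fall to 0%. The effects of device and teaching cannot be separated in one arm.

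**The case against.** The plan is open about its limits. It calls itself a pilot, says randomization is ideal, and uses a good result only to consider a randomized trial. That stands, and it is why the design and decision rule need no change. It does not supply a reason for saying that confounding is minimized.

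The teaching can fairly be read as part of the device program. It shares a sentence with device education, and Section D.III goes on to alerts at set output limits. That also stands: the teaching belongs to the package being tested. A reader might infer that it is a confounder that by itself accounts for a low count. The documents do not support that, since the Section B pathway had several components and teaching on output parameters is only part of such a pathway. What remains is that the package cannot be split. Likewise, Section F.II may be describing only post-operative management, so its mismatch with D.III calls for reconciling and is not a clear contradiction.

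The window calculation rests on an assumed stay and a constant rate. In addition, Section B attaches the post-discharge label to the overall rate, and the dehydration figure follows in the same sentence. Applying the label to both is the natural reading. The visit at 4-6 weeks could pick up later readmissions, but the aim counts only the first 30 days after surgery. So the difference in windows is documented, while its size is not.

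**Conclusion.** The statement about confounding is unsupported and should go. One documented difference, the shorter time at risk, favors a low count. Selection and the applicability of 15% are possible threats of unknown size. The result describes the package, not the device alone.

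Under the assumed stays of 3 to 10 days and a constant rate, the chance of 0 or 1 with no effect rises from 4.2% (at 15.5%; 4.8% at the planned 15%) to between 6.3% and 15.7%. This matters mainly at 1/30.

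Three stronger readings do not hold.

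- A reader might infer that 0 or 1 of 30 shows nothing beyond a rate below 15%. After 0/30 the limit is 9.5%, which excludes 10% and every window-adjusted rate in the table (chances 1.1% to 3.4%).
- A reader might infer that the comparison fails unless 15% is exactly right. It needs only a background above the observed upper limit, and a higher background would strengthen it.
- A reader might take a much lower background, such as 5% (chance of 0 or 1: 55%), as the size of the problem. The documents give no site dehydration rate, so nothing in them supports that choice.

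**What to change.** 1. Delete the sentence on minimized confounding in Section E. State instead that the result describes Ostom-i with its teaching and the resulting staff contact, in English-speaking smartphone users followed to 30 days after surgery, against an assumed historical dehydration readmission rate of 15%. Add that it neither isolates the device nor establishes its efficacy.
2. Align the aim and the primary outcome in Section C with that statement, since they now speak of evaluating efficacy and demonstrating a reduction. Reconcile the sentence on standard management in Section F.II with the additional teaching in Section D.III.
3. Report the exact one-sided 95% upper limit with the result (9.5% for 0/30, 14.9% for 1/30), and compare it with the background rate over the same window.
4. Optional, where records allow: report the site's own dehydration readmission rate in new-ileostomy patients over the same 30 days from surgery.

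The 15% test, n = 30 and the 0-or-1 rule stay as planned. Items 1 and 2 are wording, item 3 is one line of analysis, and item 4 needs a retrospective record query. The price is a narrower conclusion: 1/30 would not exclude a background rate of 10% or 12%, where the chance of 0 or 1 with no effect is 18.4% or 11.0%.
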